#### **• Background**

The prevalence of sleep-disordered breathing {SOB} in adults has been increasing. It is a common disorder, which usually requires lifelong care. A recent study has shown that in the last 2 decades, substantial increases have been seen in 30-70 year olds for both genders (1).

One of the likely leading causative factors for the increase in SOB is obesity. The ongoing obesity epidemic has given rise to other epidemics (off-spring epidemics) and the increase in SOB is one of them. (1) The increase in body mass index (BMI) can cause an increase in fat deposition and decrease in neuromuscular control of the airway, which can increase the collapsibility of the airway. (2)

SOB is associated with much co-morbidity including cardiovascular diseases, strokes, metabolic disorders and impaired neurocognitive function. {3-5} Due to the wide range and serious implications of untreated SOB, there is high motivation to treat it. The American Academy of Sleep Medicine (AASM) recommendations for treatment of OSA include: weight loss, behavioral therapy, oral appliance therapy, positive airway pressure (PAP) therapy and surgical intervention. (6) There also continues to be emerging and investigational therapies which may contribute to managing or improving SOB in the future.

PAP may be delivered in continuous positive airway pressure {CPAP}, bi-level positive airway pressure (BPAP) or auto titrating positive airway pressure (APAP) modes. The gold standard for treatment of OSA is CPAP; however, it has been shown that APAP can be better tolerated and used a greater number of hours than CPAP in long term randomized study (7, 8). CPAP improves systemic hypertension, and it has been demonstrated that successful CPAP treatment prolongs survival (9). In addition, improvements in glucose metabolism have also been shown with CPAP therapy {22}. While PAP therapy continues to be the first line therapy offered (10), adherence issues are well established. (11) A recent study following patients from 2-6 years, showed an adherence rate of 54.8% with an average use of 4.02 hours/night. (12). Adherence issues therefore may result in less favorable effectiveness than required. (13)

An alternative option for the treatment of SOB is oral appliance therapy (OAT). The AASM and the American Academy of Dental Sleep Medicine (AADSM) have provided management guidelines for the utilization of oral appliance therapy (14, 15). Although not as efficacious as CPAP, OAT is indicated for use in patients with mild to moderate OSA who prefer OAT to CPAP, or who do not respond to CPAP, are not candidates for CPAP, or who fail CPAP or behavioral measures such as weight loss or sleep position change. (15) OAT has also demonstrated cardiovascular benefits by lowering blood pressure and reducing mortality (16, 19). OAT has also been shown to have a good adherence rates as determined by mean hours of usage. One example of this is a study by Lowe and others showed an 'index of agreement' of 0.99 between the monitor clock time and the subject's log sheets. In the study, the mean hours of wear was 6.8 hours. (17)

While the benefits and good adherence of OAT are recognized, the efficacy of OAT remains less than optimal (partial response). Using a definition of decreasing Apnea-Hypopnea Index (AHI) to less than or equal to 10, it has been shown that the percent success rates for OAT was: Mild OSA-81%, Moderate OSA-60% and Severe OSA-25%. The mean success rate of OAT was 52% (18).

It would seem prudent that the simultaneous use of both CPAP and OAT (combination therapy) may be beneficial to consider. One pilot study has shown that combination therapy can reduce CPAP pressure (as compared to original PAP titration study) and improve effectiveness of OAT (20). Another study was able to show that OAT could be a short-term alternative to CPAP (21). The study demonstrated that an oral appliance could be as successful, or near successful as CPAP, and as being a convenient option for travel purposes.

There are two primary ways to use combination therapy. One way uses the oral appliance as an anchor for a customizable nasal mask interface (CNMI) while another way uses the patient's preferred CPAP mask separate from the oral appliance. This study will prospectively and randomly assign patients to one of the two combination therapy options and they will use each one for two months. Clinical data obtained during the study will be at one month and at the end of two months and will include: AHI, CPAP pressure, and mask leakage, Nadir, T90, hours of usage and ESS.

### **Criteria for Subject Selection**

- Number of subjects: 50-100
- Gender of Subjects: Male and female with attempt of equal participation
- Age of Subjects: 18 and older
- Racial and Ethnic Origin: Distribution will mirror that of normal patient base of the clinics which is primarily Hispanic.
- Inclusion Criteria: Diagnosis of OSA with AHi greater than or equal to 5, CPAP intolerance due to CPAP pressure too high, mask fit/leak, Oral Appliance Therapy partial responders of AHi at or above 5, patients demonstrated successful adherence to oral appliance therapy.
- Exclusion Criteria: Daily use of alcohol, CNS depressants and narcotics, pregnancy and prisoners

- Vulnerable Subjects: Ethnic minorities and economically disadvantaged

## Methods and Procedures

At least fifty patients who were intolerant to CPAP and had a partial response to OAT (AHI greater than or equal to 5 will be recruited randomly and prospectively into one of two groups (at least 25 each in each group). The group options were: 1} Combination therapy with CNMI and 2) Combination therapy with patient's preferred CPAP mask.

These CPAP intolerant patients underwent a PAP titration during an overnight PSG or were assigned an autoPAP and had accumulated at least one month of data. Intolerance to CPAP was defined as patients who reported to their sleep physician that they were intolerant due to CPAP pressure, mask fit/leak issues. They were also asked to fill out a CPAP intolerance questionnaire to document the reason for the intolerance.

Patients who were determined to be partial responders to OAT were determined to have met an adherence and titration protocol. Adherence was defined as using the oral appliance for at least 4 hours per night for 70% of the nights in the 30-day period leading up to the study. The titration protocol includes a minimum of one month of titration along with using patient testimony, bed partner testimony and overnight oximetry to aid in the titration and when tested with an HST or in-lab PSG, the AHI was greater than or equal to 5 (verification sleep test).

Patients who were assigned the option of using their previously preferred CPAP mask, they underwent one CPAP care session and then the two month time period would begin.

If patients were assigned the CNMI option, they were allowed one week for follow up/adjustments of the customized mask, they also underwent one CPAP care session and then the two month time period would begin.

► Data Analysis and Data Monitoring - Data will be analyzed quantitatively using, but not limited to, the Kolmogorov-Smirnov test, Student's *t* test or the Wilcoxon rank- sum test, and SPSS 12.0 for Windows {Chicago, IL, USA}).

Demographic: Ask patients for age and gender

Physiologic: Weight Scale - Weight+ Ruler - Height= Body mass index (BMI)

Pulse Oximeter: Nadir (low O2 saturation), Time percent below 90 {T90}

Polysomnography {PSG}: Apnea-Hypopnea Index (AHI), CPAP pressure, leakage

CPAP Airview or Data Card: AHI, CPAP pressure, leakage

Home Sleep Study (HST): AHI, Nadir, and T90

► Data Monitoring - At time of start of study at [name] Dental Sleep Medicine, PLLC or at J. [name], P.A. Obtain from patient:

- 1) CPAP intolerance questionnaire
- 2) Compliance questionnaire with oral appliance
- 3) Obtain CPAP data from PAP titration or autoPAP: CPAP pressure, Leakage, Apnea-Hypopnea Index (AHi), Nadir, Time percent below 90 (T90), hours of usage
- 4) Home Sleep Test (HST): AHi, Nadir, T90
- 5) AutoPAP: AHi, mask leakage
- 6) Gather patient demographics: age, gender, BMI

At one (1) Month

- 1) CPAP intolerance questionnaire
- 2) Compliance questionnaire with Oral Appliance
- 3) Gather CPAP data from "Airview" or Data card: CPAP pressure, leakage, AHi,
- 4) Gather oxygen saturation data from Pulse Oximeter: Nadir and T90
- 5) Optional verification (PSG or HST)

After 2nd Month

- 1) CPAP intolerance questionnaire
- 2) Compliance questionnaire with Oral Appliance
- 3) Gather CPAP data from "Airview" or Data card: CPAP pressure, leakage, AHi,
- 4) Gather oxygen saturation data from Pulse Oximeter: Nadir and T90
- 5) Optional verification (PSG or HST)

- Data Storage and Confidentiality- Data will be safeguarded by assigning study participants anonymous identification numbers. Depending on relevant data, it will be stored in a password protected computer with encrypted files in the sleep lab at the Pulmonary & Sleep Center of the Valley to which sub-investigator, [name] may access. At [name], D.D.S., PA and [name] Dental Sleep Medicine, PLLC facilities data will be on a password protected computer with encrypted files to which [name] and research coordinator [name] may access.
- Transition from Research Participation - subjects are patients of record of the clinics.

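### The reason for CPAP intolerance is recorded at the start and bears on the randomised interface, but no named between-arm comparison uses it; adjust for it and report by reason descriptively.

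*Combined protocol and SAP*

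**What the plan says.** Criteria for Subject Selection lists "CPAP intolerance due to CPAP pressure too high, mask fit/leak" among the inclusion criteria. Methods and Procedures defines intolerance as the patient's report to the sleep physician of being "intolerant due to CPAP pressure, mask fit/leak issues". I read both as admitting either reason.

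The same section states that patients "will be recruited randomly and prospectively into one of two groups (at least 25 each in each group". It names no randomisation method and no stratification factor. One arm receives the customisable nasal mask interface (CNMI), with a week for adjustment and one CPAP care session. The other is described by "Patients who were assigned the option of using their previously preferred CPAP mask", also with one care session. The Background explains that this mask is worn separately from the oral appliance. No text says whether it is the mask on which the patient became intolerant.

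The reason is recorded: "They were also asked to fill out a CPAP intolerance questionnaire to document the reason for the intolerance". The questionnaire is listed again at the start of the study, at one month and after the second month.

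The analysis text is one sentence in Methods and Procedures. It names a Kolmogorov-Smirnov test, a t test or a rank-sum test, and says that the list is not exhaustive. It names no covariate, stratum or subgroup, and no use for the questionnaire.

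**The concern.** In this trial the entry reason overlaps the thing randomised. Both arms use the oral appliance, and the Background cites a pilot study in which combination therapy lowered CPAP pressure, so a patient who could not tolerate the pressure might gain in either arm. A patient whose difficulty was mask fit or leak is assured of a new interface only in the CNMI arm. Leakage is itself a listed outcome, and the stated purpose includes tolerance to CPAP.

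Two things are at stake. If the reason predicts leakage, AHI or hours of usage, ignoring it leaves avoidable noise in a small comparison. If the arm effect differs by reason, the overall difference is an average over whatever mix is recruited, and a reader needs to know that mix to apply the result.

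**Working it through.** The documents give no primary outcome, effect size, SD or power, so there is no stated figure to reproduce. What follows is illustration, in SD units (SD within reason level = 1).

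**Inputs.** From the documents: at least 25 per arm (Methods and Procedures) and 50 to 100 in total (Criteria for Subject Selection). Assumed: simple randomisation; a 50% mask fit/leak share unless stated; a reason effect on outcome, d, of 0.5 to 1.0 SD; two-sided 5% level.

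**1. Chance imbalance and its size.**
- SD of the between-arm difference in share = sqrt(2 × 0.5 × 0.5 / n). For n = 25 this is 0.141, a 95% range of about ±28 points. For n = 50 it is 0.10.
- The exact binomial chance that the arms differ by 20 points or more is 20% at 25 per arm and 6% at 50 per arm.
- At the edge of the range with 25 per arm, the shift in the arm difference is 0.28 × 0.5 = 0.14 SD to 0.28 × 1.0 = 0.28 SD.

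**2. What the unadjusted standard error already contains.**
- Variance of the unadjusted difference at 25 per arm = 2/25 + d² × 0.141² = 0.08 + 0.02d².
- d = 0.5: 0.08 + 0.005 = 0.085, SE 0.292.
- d = 1.0: 0.08 + 0.02 = 0.10, SE 0.316.
- Adjusted, ignoring the small cost of estimating the covariate: 0.08, SE 0.283.

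The 0.02d² term is the chance imbalance, and the unadjusted test counts it. Adjustment removes it. The SE falls by about 3% (0.283/0.292 = 0.97) to 11% (0.283/0.316 = 0.89). Put another way, the unadjusted 25 per arm do the work of 25 × 0.08/0.085 = 23.5 to 25 × 0.08/0.10 = 20 adjusted. If d = 0 there is no gain.

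**3. Dependence on the mix.**
- Overall effect = m × (effect in mask fit/leak patients) + (1 − m) × (effect in pressure patients), where m is the mask fit/leak share.
- Effects 0.8 and 0 (assumed): 0.30 × 0.8 = 0.24 at m = 30%, and 0.70 × 0.8 = 0.56 at m = 70%.
- Effects 0.5 and 0.5 (assumed): 0.50 at every m.

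So dependence on the mix comes wholly from the assumed difference in effect.

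**4. What results by reason can show.** With 25 per arm and a 50% share there are about 12 per arm per level.
- Half-width within a level = t(0.975, 22) × sqrt(2/12) = 2.074 × 0.408 = 0.85 SD.
- Half-width for the interaction = t(0.975, 44) × sqrt(4/12) = 2.015 × 0.577 = 1.16 SD.
- Power of an interaction test for 0.8 versus 0 is about 29% at 25 per arm and 52% at 50 per arm.

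**The case against.** The strongest reply is that nothing is biased. Randomisation gives a fair average for the enrolled patients, and every trial's average depends on its mix if some baseline factor modifies the effect. The shift of 0.14 to 0.28 SD from imbalance is a worst-case edge. It is no more than about one standard error (0.28 SD), against a 95% half-width of about 0.57 SD, and it is smaller still at 50 per arm. All of this stands. Leaving the factor out does not raise the false-positive rate above its nominal level.

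A reader might also infer that a CNMI advantage would mean only that patients failed their old mask a second time. The documents do not support that. In the comparison arm the mask is worn with an oral appliance and after a care session, and the Risk/Benefit Assessment adds follow-up within a week of delivery. A previously preferred mask need not be the one that failed. That arm may resemble the earlier situation, but it is not shown to repeat it.

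Three further points have weight. The list of tests is open-ended, so adjustment is allowed, though none is prespecified. The questionnaire's content is not given and patients may name both reasons, so any classification has to be written down in advance. And the absence of a primary outcome and a stated primary comparison is a larger gap than this one. None of these removes the case for using a baseline factor that is already recorded and is closely tied to the randomised interface.

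**Conclusion.** The point holds as a modest, inexpensive improvement to the analysis. Both reasons for intolerance are eligible, the interface is what is randomised, the reason is recorded at the start, and the named tests do not use it. The unadjusted comparison remains valid on average for the enrolled mix. The loss is precision: about 3% to 11% of the standard error at 25 per arm, if the reason shifts the outcome by 0.5 to 1.0 SD and half the patients name mask fit or leak. Those inputs are assumptions, and the loss is nil if the reason does not predict outcome.

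Dependence on the mix is plausible but unquantified. The 0.24 to 0.56 SD range rests entirely on assumed effects of 0.8 and 0. A reader might also expect results by reason to separate a general benefit of CNMI from one confined to patients with mask problems. At this size they cannot: the within-level half-width of 0.85 SD exceeds the assumed 0.8 SD effect.

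**What to change.** Before the data are examined, add the following to the analysis text in Methods and Procedures.

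- Define a two-level baseline factor from the start-of-study CPAP intolerance questionnaire: mask fit/leak named (including patients who name both reasons) versus pressure only.
- For the between-arm comparisons of leakage, AHI and hours of usage, fit a linear model with arm, this factor and, where collected, the baseline value of the outcome. Use a transformed or rank-based version if the outcome is skewed. State which baseline source is used, because the start-of-study list gives AHI under more than one test.
- Report the factor's distribution by arm. Report the arm difference within each level and the interaction, each with a 95% interval, all labelled descriptive.
- State that any overall conclusion applies to the enrolled mix.

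The cost is one or two degrees of freedom, one table and a written classification rule. The factor needs no new data. Hours of usage are promised in the Background but not shown in the one-month and two-month lists, so their collection should be confirmed. The downside is wide intervals by reason, which must not be read as evidence for or against a difference in effect. The choice of mask for patients is not at issue.

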## **"Comparison of Two Techniques of Combination Therapy for Treatment of OSA "**

### **Purpose of the study and background**

#### **• Purpose of the study**

To compare two techniques of combination therapy for obstructive sleep apnea (OSA) and determine if clinical data obtained before, during and after suggests that either or both techniques improve tolerance to CPAP and/or are statistically more efficacious than CPAP or oral appliance therapy alone.

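### A gain over the earlier CPAP-alone record also contains a protocol-prescribed CPAP care session, so it cannot be credited to combination therapy alone

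*Combined protocol and SAP*

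**What the plan says.** The Purpose section sets out to determine whether "either or both techniques improve tolerance to CPAP and/or are statistically more efficacious than CPAP or oral appliance therapy alone". Methods and Procedures defines two randomised groups, and both are combination therapy: "The group options were: 1} Combination therapy with CNMI and 2) Combination therapy with patient's preferred CPAP mask". There is no CPAP-alone group.

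The CPAP-alone information is historical. Patients "underwent a PAP titration during an overnight PSG or were assigned an autoPAP and had accumulated at least one month of data", and the start-of-study list takes the data from that source: "Obtain CPAP data from PAP titration or autoPAP: CPAP pressure, Leakage", followed by AHI, nadir, T90 and hours of usage.

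Between that record and the first outcome, the protocol adds a step in both arms. Patients assigned to the preferred-mask option are described as "using their previously preferred CPAP mask, they underwent one CPAP care session and then the two month time period would begin". CNMI patients have a week for adjusting the customised mask, and "they also underwent one CPAP care session and then the two month time period would begin". Outcomes follow at one month and after the second month. Nothing on the start-of-study list asks what CPAP support came before the earlier record.

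**The concern.** A before-after comparison with CPAP alone should differ from its reference by the technique under study. Here it differs by the technique and by a care session that is part of neither technique. Patients enter because of CPAP pressure or mask fit and leak. These are complaints that CPAP support might ease with no contribution from the oral appliance. The follow-up measures include leak, device AHI, CPAP pressure and an intolerance questionnaire, and the Background adds hours of usage.

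At stake is the part of the objective that names CPAP alone. If the protocol is followed exactly, an improvement due partly to the session would be reported as combination therapy outperforming CPAP. No CPAP-alone period follows the session, and the analysis paragraph names no method that would separate its effect.

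**Working it through.** **Order of events (Methods and Procedures, and its data monitoring lists)**

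| Step | Preferred-mask arm | CNMI arm |
|---|---|---|
| CPAP-alone record | earlier titration night, or at least one month of autoPAP | same |
| After assignment | one CPAP care session | one CPAP care session; custom mask with a week of adjustments |
| Outcomes | one and two months, on combination therapy | same |

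**What each comparison contains**

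- Preferred-mask arm against the earlier record: technique + care session.
- CNMI arm against the earlier record: technique + care session. The Background describes this technique as anchoring the mask on the appliance, so the mask is inside the technique.
- CNMI against preferred mask: difference between techniques. The session occurs on both sides and does not by itself bias the contrast.

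**Outcomes most exposed.** Leak and reported tolerance are closest to what CPAP support could change. Hours of use is exposed only where an autoPAP record exists, because a single titration night gives no home-use reference. For AHI and pressure the link is less direct.

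**Size, as an illustration.** The documents state no alpha, SD, expected effect or sample-size calculation, so there is no figure of the plan's own to reproduce.

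Inputs from the documents: n = 25 (minimum per group) and n = 50 (minimum total, both arms pooled).

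Assumptions: two-sided 5% test; no true contribution from the technique; the session alone shifts an outcome by d = 0.1, 0.2 or 0.3 SD of within-patient change.

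Paired t test: P(false benefit) = P(T > t(0.975, n−1)), where T is noncentral t with n−1 degrees of freedom and noncentrality d√n.

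- n = 25: critical value 2.064; d√n = 0.1×5 = 0.5, 0.2×5 = 1.0, 0.3×5 = 1.5.
- n = 50: critical value 2.010; d√n = 0.1×7.07 = 0.71, 0.2×7.07 = 1.41, 0.3×7.07 = 2.12.

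The protocol does not name a paired test, so the same shifts were also put through a two-sample t test on the before and after values. This was done by simulation with an assumed within-patient correlation of 0.5. At that correlation the SD of change is √(2×(1−0.5)) = 1 times the SD of a single measurement, so d is on the same scale in both rows.

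| Test | n | d = 0.1 | d = 0.2 | d = 0.3 |
|---|---|---|---|---|
| Paired t | 25 | 6.9% | 15.9% | 30.2% |
| Paired t | 50 | 10.3% | 28.3% | 54.8% |
| Two-sample t | 25 | about 1% | about 4% | about 10% |
| Two-sample t | 50 | about 2% | about 9% | about 25% |

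With no shift, the paired test gives 2.5% in the favourable direction. With either test, the chance of misattribution rises with sample size.

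**The case against.** **The mask.** A reader might infer that the new custom mask is a second rival explanation in the CNMI arm, so that a CNMI gain over CPAP alone is doubly confounded. The documents do not support that. The Background makes the mask anchored on the appliance the technique itself, and the Purpose asks whether either technique does better than CPAP. It does not ask what an appliance adds with the mask held constant. A gain from the mask is therefore correctly credited to the CNMI technique. What remains is narrower: a CNMI gain cannot be read as the effect of merely adding an appliance to CPAP.

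**Prior support is unknown.** The content of the care session is not described, nor is the support that preceded the earlier record. If the original titration or autoPAP set-up included comparable help, the difference shrinks. This stands, and it makes the concern conditional.

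**Direction.** For patients whose reference is one laboratory night, home data after a care session need not look better than that night. This stands too. The calculation models favourable shifts only, and the documents do not show that the session will produce one.

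**Test and size.** The paragraph on analysis names Student's t test or the Wilcoxon rank-sum test, as a non-exclusive list. With a two-sample test the false-benefit figures fall to roughly a third or less of the paired ones at n = 25. The numbers are therefore illustrative.

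**Overlap.** The session is one of several before-after differences that follow from having no concurrent CPAP-alone arm; the education and troubleshooting promised under Risk/Benefit Assessment are others. That is fair. The session still merits its own point, because the protocol prescribes it between reference and outcome, and a newer CPAP record would not remove it unless it too followed comparable support.

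**Conclusion.** The concern holds in a limited form. The only CPAP-alone reference predates a CPAP care session that every patient receives and that is part of neither technique. Unless the reference already followed comparable support, a before-after gain may come partly from the session and cannot be attributed to combination therapy alone. It applies chiefly to leak, reported tolerance and, for patients with autoPAP records, hours of use.

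The size cannot be fixed from the documents. For assumed shifts of 0.1 to 0.3 SD at n = 25, false benefit ranges from about 7% to 30% with a paired t test and from about 1% to 10% with a two-sample t test at an assumed correlation of 0.5.

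A reader might also infer that the trial as a whole is compromised. It is not: the session is given in both arms and leaves the randomised comparison of CNMI with the preferred mask unbiased on this account. The change should be made, because it alters what may be concluded about one named objective.

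**What to change.** 1. Add one field to the start-of-study list, filled from clinic records: whether the CPAP-alone record was obtained after a comparable CPAP care session (yes, no, unknown). Report the before-after result descriptively by that field, without testing. Restricting the comparison further, for example to mask-matched patients within one arm of 25, would leave groups too small to be useful.
2. State in the Purpose section and in the analysis paragraph that any gain over the earlier CPAP record is attributed to the technique plus a CPAP care session, not to the technique alone. Add that a CNMI gain is not an estimate of adding an appliance to CPAP.
3. Rest the confirmatory conclusion on the randomised between-arm comparison.

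Cost: one data field, one descriptive table and a few sentences. No new arm or visit and no change in care is needed. The downside is a weaker claim against CPAP alone.

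### The efficacy objective against CPAP or oral appliance alone needs a within-patient comparison, but the plan ties no paired test to it and does not fix the reference records

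*Combined protocol and SAP*

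**What the plan says.** - **Objective** (Purpose of the study): to determine whether "either or both techniques improve tolerance to CPAP and/or are statistically more efficacious than CPAP or oral appliance therapy alone".
- **Design** (Methods and Procedures): two randomised groups of at least 25. One uses the customised nasal mask anchored to the appliance (CNMI), the other the patient's preferred CPAP mask with the appliance. Neither receives a single therapy.
- **Tests** (the analysis paragraph in Methods and Procedures): the one relevant sentence is "Data will be analyzed quantitatively using, but not limited to, the Kolmogorov-Smirnov test, Student's *t* test or the Wilcoxon rank- sum test". No endpoint, contrast, time point or pairing is given.
- **Selection**: the inclusion criteria require "Oral Appliance Therapy partial responders of AHi at or above 5". Methods and Procedures adds that "when tested with an HST or in-lab PSG, the AHI was greater than or equal to 5 (verification sleep test".
- **CPAP history** (Methods and Procedures): patients "underwent a PAP titration during an overnight PSG or were assigned an autoPAP and had accumulated at least one month of data".
- **Start-of-study records** (Data Monitoring): item 3 is "Obtain CPAP data from PAP titration or autoPAP: CPAP pressure, Leakage, Apnea-Hypopnea Index (AHi), Nadir, Time percent below 90 (T90), hours of usage", item 4 is "Home Sleep Test (HST): AHi, Nadir, T90", and item 5 lists autoPAP AHI and mask leakage again.
- **Follow-up records at months 1 and 2**: pressure, leakage and AHI come from Airview or a data card, and nadir and T90 from a pulse oximeter. A sleep test is listed only as "Optional verification (PSG or HST".

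**The concern.** With no single-therapy group, each patient's earlier record is the only comparator that the protocol supplies. Two choices then decide the result: which test is used, and which earlier record counts as CPAP alone or oral appliance alone. The plan makes neither, so both can be made after the data are seen.

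The test matters because an independent-sample test ignores the within-patient correlation and usually wastes power. The record matters because patients enter with an on-appliance AHI of 5 or more. If that same test serves as the oral-appliance baseline, some of the later fall is expected without any treatment effect, and pairing does not remove it.

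This point covers the efficacy part of the objective. Tolerance is outside it.

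**Working it through.** **No planned figure to reproduce.** The sample size of 50-100 comes with no alpha, power, effect size, SD or correlation, so it cannot be rebuilt. The calculations below are illustrations with n = 25 (the stated minimum per group) and two-sided 5%. Correlations, SD ratios and the AHI distribution are assumptions, because the documents give none.

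**1. Paired versus independent-sample tests on before/after data.** Set the baseline SD to 1, the follow-up SD to k and the correlation to ρ. The SD of the difference is √(1 + k² − 2ρk). A paired t test with n = 25 has 80% power for an effect of 0.584 times that SD (noncentral t). An independent-sample test uses a standard error too large by √[(1 + k²)/(1 + k² − 2ρk)]. For k = 1 and ρ = 0.5 this is √(2/1) = 1.41.

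Simulated power for that same effect:

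| SD ratio k | Test | ρ = 0.1 | 0.3 | 0.5 | 0.7 |
|---|---|---|---|---|---|
| 1 | unpaired t | 79% | 70% | 54% | 26% |
| 1 | rank-sum | 76% | 66% | 49% | 24% |
| 0.5 | unpaired t | 79% | 73% | 63% | 47% |
| 0.5 | rank-sum | 76% | 69% | 59% | 43% |
| 0.3 | unpaired t | 80% | 76% | 71% | 64% |
| 0.3 | rank-sum | 75% | 71% | 65% | 59% |

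The signed-rank test has about 76-79% throughout. The actual type I error of unpaired t runs from 0.1% to 4.7%. Rank-sum is also mostly conservative, but reaches 6.1% at k = 0.3, ρ = 0.1.

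**2. Which record is the reference?**

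| Reference | Candidate at study start | What is not stated |
|---|---|---|
| CPAP alone | Item 3, CPAP data by its own wording | Whether a patient's record is a titration night or at least a month of autoPAP; how item 5 relates to it |
| Oral appliance alone | Item 4, the HST | Whether the appliance was in place; whether it is the verification test used for selection, which could also be an in-lab PSG |

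Month-2 AHI is device-derived unless the optional test is done. Against oral appliance alone, it is therefore compared with an HST or PSG value.

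**3. Regression to the mean, oral-appliance contrast only.** Assume log-normal AHI with median m, log-SD 0.8 and retest correlation r; keep patients with a first value of 5 or more; assume no true change. With a = ln(5/m)/0.8 and λ = φ(a)/[1 − Φ(a)], the expected geometric-mean ratio is exp[−(1 − r) × 0.8 × λ].

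For m = 8: a = −0.588 and λ = 0.465. At r = 0.5 the ratio is exp(−0.5 × 0.8 × 0.465) = 0.83, a 17% fall with no effect.

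Share of n = 25 samples in which a paired t test on log AHI falsely shows improvement (nominal 2.5%):

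| Median before selection | r = 0.5 | 0.7 | 0.9 |
|---|---|---|---|
| 8 | 22% | 15% | 7% |
| 12 | 9% | 7% | 5% |

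**4. Arm comparison, 25 per group.** The unadjusted detectable difference at 80% power is 0.81 SD. ANCOVA multiplies the variance by (1 − ρ²)(N − 3)/(N − 4) with N = 50. At ρ = 0.5 this is 0.75 × 47/46 = 0.766, and 0.809 × √0.766 = 0.71 SD. At ρ = 0.1/0.3/0.7 the result is 0.81/0.78/0.58 SD.

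**The case against.** The strongest reply is that the plan commits no wrong test. Student's t can be paired, the list is open-ended, and the rank-sum test suits the comparison of the two techniques. This stands: the power figures show what is at risk if independent-sample tests are used, not a loss already built in. For unpaired t at correlation 0.1 the loss is almost nil.

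Four other limits stand.

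- Item 3 is recognisable as CPAP data, so it would be wrong to say that no reference can be identified. Where its source is autoPAP, baseline and month-2 AHI are both device-derived.
- A reader might infer that regression to the mean undermines every before/after contrast. It does not follow: patients are selected on treated AHI only for the oral appliance, whereas CPAP intolerance is self-reported.
- A reader might start from a lower median. At 5 the false-improvement rates are 55/35/14%. But with log-SD 0.8 that median puts Φ(ln 2/0.8) = 81% of patients at AHI 10 or less, which is the success rate that the Background quotes for mild OSA alone. The overall 52% quoted there corresponds to a median near 9.6 and rates of about 15/10/6%. Entry is not limited to mild disease.
- CPAP pressure and leakage belong with intolerance as the protocol defines it, so they should not be counted among the efficacy contrasts.

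It can also be said that baseline adjustment of the arm comparison is mere preference. The unadjusted tests are indeed valid there. But the baseline values are already collected, and using them costs one degree of freedom.

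**Conclusion.** The concern holds as a gap in specification. A stated objective has no test tied to it and no fixed reference record, and the only non-parametric location test named does not fit paired data. The documents do not support the stronger reading that the plan prescribes the wrong test or rules out pairing.

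With 25 patients and equal spreads, the cost of independent-sample tests runs from about 1 to 54 percentage points of power for unpaired t, and less if treatment narrows the spread. Reusing the selecting test would raise false improvement in the oral-appliance contrast to between 5% and 22% at medians of 8 to 12, and higher only if the population is close to all mild. All of these sizes rest on assumed correlations and distributions.

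Pairing recovers power, but the before/after contrast remains uncontrolled. The sponsor should settle this before analysis.

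**What to change.** **In Methods and Procedures, state:**

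1. The efficacy objective is tested within patients, month 2 versus study start, for AHI, nadir and T90. Use a paired t test for nadir and a Wilcoxon signed-rank test for AHI and T90, each with a 95% CI and a stated rule for zeros and ties. Do this separately against the CPAP-alone and oral-appliance-alone references. Name one contrast as primary for each technique, with Holm adjustment over the two.
2. CNMI versus preferred mask at month 2 is analysed by ANCOVA, adjusted for the study-start value of the same measure from item 3, with rank ANCOVA for skewed measures.

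**In the start-of-study list:** name item 3 as the CPAP-alone reference and record each patient's source (titration or autoPAP). Name the on-appliance HST or PSG as the oral-appliance-alone reference, and say whether it is the test used for selection.

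**As limitations:** state that the before/after contrast is uncontrolled, and that the oral-appliance AHI contrast sets HST or PSG against device-derived AHI unless the optional test was done.

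**Reconcile first:** the last paragraph of the Background can be read as each patient using both options for two months, whereas Methods and Procedures describes two groups and one two-month period. Part 2 assumes parallel groups.

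**Cost:** no new visits. ANCOVA uses one degree of freedom and gains nothing at correlation 0.1. Some patients may lack the named source, so some contrasts may have fewer than 25 per group.
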